3.3.2 Rationale for Patient Population

The safety and efficacy of baloxavir marboxil has been investigated in otherwise healthy adult and adolescent populations, *and in adult and adolescent patients at high risk of influenza-related complications. Baloxavir marboxil has been approved in several*

countries, including Japan and the United States. Given the significant unmet need in patients hospitalized with *severe* influenza, this study is designed to evaluate the efficacy and safety of baloxavir marboxil in this population.

Baloxavir marboxil has been well tolerated in adults and adolescents in previous studies, with a pharmacokinetic (PK) profile supportive of the inclusion of these age groups in this study. *There are a number of pediatric studies in progress that are designed to confirm the safety and pharmacokinetics of baloxavir marboxil in otherwise healthy children with influenza aged < 12 years. Depending on the outcome of these additional pediatric studies and this current study in hospitalized patients, younger hospitalized patients may be studied in a future protocol.*

Morbidity and mortality are particularly high for elderly patients and immunocompromised patients admitted to hospital with influenza. This study will, therefore, include both of these groups, with no upper age limit or restriction on the degree of immunocompromise. Patients with severe renal or severe liver impairment will be excluded based on the current unknown PK profile and tolerability of repeated doses of baloxavir marboxil.

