4.1.1 Inclusion Criteria

Patients must meet the following criteria for study entry:

- Adult patients: Signed informed consent by any patient capable of giving consent, or, where the patient is not capable of giving consent, by his or her legal/authorized representative
- Adolescent patients not able to legally consent: written informed consent for study participation is obtained from patient’s parents or legal guardian, with assent as appropriate by the patient, depending on the patient’s level of understanding and capability to provide assent
- Age \geq 12 years at the time of signing the Informed Consent Form/Assent Form
- Ability to comply with the study protocol, in the investigator’s judgment
- Patients who require hospitalization for severe influenza or acquire influenza during hospitalization, the severity of which requires an extension of hospitalization
- Diagnosis of influenza A and/or B by a positive Rapid Influenza Diagnostic Test (RIDT) or reverse transcriptase-polymerase chain reaction (RT-PCR)

Positive results from local tests are acceptable if conducted within the 24 hours prior to screening.

A patient with a negative RIDT may be enrolled if influenza is suspected based on local surveillance data or if the patient reports contact with a known case of influenza within the prior 7 days and all other inclusion criteria are met

- The time interval between the onset of symptoms and randomization is within 96 hours

The onset of symptoms is defined as the time when the patient experiences at least one new general symptom (e.g., headache, feverishness or chills, muscle or joint pain, fatigue), respiratory symptom (e.g., cough, sore throat, nasal congestion), or fever.

- A score of ≥ 4 based on the NEWS2 (see [Appendix 3](#))
- Patients will require objective criteria of seriousness defined by at least one of the following criteria:
 - Requires ventilation or supplemental oxygen to support respiration
 - Has a complication related to influenza that requires hospitalization (e.g., pneumonia, CNS involvement, myositis, rhabdomyolysis, acute exacerbation of chronic kidney disease, asthma or chronic obstructive pulmonary disease [COPD], severe dehydration, myocarditis, pericarditis, exacerbation of ischemic heart disease)
- For women of childbearing potential: Agreement to remain abstinent (refrain from heterosexual intercourse):

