4.1.2 Exclusion Criteria

Patients who meet any of the following criteria will be excluded from study entry:

- Patients who have received more than 48 hours of antiviral treatment for *the current influenza infection* prior to screening
- Patients who have received baloxavir marboxil for the current influenza infection
- Known contraindication to neuraminidase inhibitors
- Patients hospitalized for exclusively social reasons (e.g., lack of caregivers at home)

- Patients expected to die or be discharged within 48 hours, according to the investigator's judgement
- Patients weighing <40 kg
- Patients with known severe renal impairment (estimated glomerular filtration rate <30 mL/min/1.73 m²) or receiving continuous renal replacement therapy, hemodialysis, peritoneal dialysis
- Patients with any of the following laboratory abnormalities detected within 24 hours prior to or during screening (according to local laboratory reference ranges:
 - ALT or AST level > 5 times the upper limit of normal (ULN)
 - OR
 - ALT or AST > 3 times the ULN and total bilirubin level > 2 times the ULN
- Pregnant or breastfeeding, or positive pregnancy test in a predose examination, or intending to become pregnant during the study or within 28 days after the last dose of study treatment
- Exposure to an investigational drug within 5 half-lives or 30 days (whichever is longer) of randomization
- Any serious medical condition or abnormality in clinical laboratory tests that, in the investigator's judgment, precludes the patient's safe participation in and completion of the study
- *Known hypersensitivity to baloxavir marboxil or the drug product excipients*

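### Protocol 3.3.2 says severe liver impairment is excluded, but the exclusion list tests only for raised transaminases; how the renal limit is to be assessed is also left open

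*Protocol*

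**What the plan says.** The rationale for the patient population (Protocol 3.3.2) states: "Patients with severe renal or severe liver impairment will be excluded based on the current unknown PK profile and tolerability of repeated doses". The sentence carries no qualification.

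The operative list is Protocol 4.1.2, repeated in the protocol synopsis and in SAP Appendix 1. It contains:

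- **Liver.** The criterion opens with "Patients with any of the following laboratory abnormalities detected within 24 hours prior to or during screening" and has two limbs. The first is ALT or AST above 5 × ULN. The second is "ALT or AST > 3 times the ULN and total bilirubin level > 2 times the ULN".
- **Kidney.** "Patients with known severe renal impairment (estimated glomerular filtration rate <30 mL/min/1.73 m²) or receiving continuous renal replacement therapy"; hemodialysis and peritoneal dialysis are listed as well.
- **General.** "Any serious medical condition or abnormality in clinical laboratory tests that", in the investigator's judgement, makes safe participation and completion impossible.

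Protocol 4.5.8 requires liver chemistry to be reviewed before each dose and points to Appendix 4 for the limits. Both 4.5.8 and 4.5 make dosing depend on the clinical assessment as well as the laboratory values.

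**The concern.** The reason given in 3.3.2 is a safety one: the pharmacokinetics and tolerability of repeated doses are unknown in these two groups. It bears directly on this design. Figure 1 gives every patient at least two doses. Section 3.3.1 cites a half-life of about 70 hours and simulated accumulation by the third dose of about 1.5-fold for peak and 1.7-fold for trough concentration. Section 5.1 then relies on the eligibility criteria to keep out patients at higher risk of toxicity.

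If the list does not identify one of the groups that the rationale names, the population that may be randomised and repeatedly dosed is wider than the one described in the benefit–risk argument. A report could not then state that severe hepatic impairment was excluded by design. With about 250 sites, anything left to discretion will also be applied unevenly.

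**Working it through.** No figure is attached to this point, so the check sets the sections side by side.

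**Liver**

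1. Population named in 3.3.2: severe liver impairment.
2. Exclusion limb 1 (4.1.2) needs ALT or AST > 5 × ULN.
3. Exclusion limb 2 (4.1.2) needs ALT or AST > 3 × ULN together with bilirubin > 2 × ULN.
4. Appendix 4 has three criteria: AST or ALT > 5 × ULN; AST or ALT > 3 × ULN with raised bilirubin or INR; AST or ALT > 3 × ULN with compatible signs or symptoms. On the natural reading each needs a raised transaminase. If the second were parsed so that INR alone sufficed, it would still apply only where INR is measured, and INR is not in the section 4.5.7 panels.
5. Take a patient with severe chronic liver impairment and ALT and AST at or below 3 × ULN. Limb 1 is not met. Limb 2 is not met whatever the bilirubin. No transaminase threshold in Appendix 4 is met.
6. No other listed criterion refers to hepatic impairment, cirrhosis, decompensation, albumin, INR or bilirubin alone. What remains is the general investigator-judgement exclusion and the clinical assessment before dosing.

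The list therefore screens for hepatocellular injury, which is not the same group as severe loss of liver function.

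**Kidney**

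1. Population named in 3.3.2: severe renal impairment.
2. The list gives a numeric limit (eGFR < 30 mL/min/1.73 m²) and adds renal replacement therapy, but qualifies the eGFR limb by *known*, which is not defined.
3. Creatinine is in the chemistry panel (4.5.7), and full chemistry is scheduled at screening (Appendix 1).
4. No section says that eGFR must be calculated from that creatinine for eligibility. The liver criterion in the same list, by contrast, is tied to results at screening or in the 24 hours before it.
5. Inclusion criterion 4.1.1 gives "acute exacerbation of chronic kidney disease" as an example of a qualifying complication. For such patients an eGFR already on file may be out of date, so which value counts is a practical question.

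**Statistical quantities.** Nothing here enters the calculation behind 264 mITTI patients or 366 randomised. Alpha and power do not change, and screen failures arise before randomisation.

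**The case against.** The strongest defence is that the transaminase and bilirubin rule is how the protocol meant to implement the liver half of 3.3.2, and that 3.3.2 is only rationale while 4.1.2 governs. That is a plausible account of intent. It would be wrong to infer that the list has no liver exclusion. What stands is that the rule selects a different group from the one 3.3.2 names.

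A second defence is that safeguards exist, and this also stands in part. The investigator-judgement exclusion expressly covers laboratory abnormalities, and dosing requires an acceptable clinical assessment. A reader might infer that a patient who meets no Appendix 4 criterion passes the Day 1 check, or that a site following the list literally would randomise such a patient. Neither follows: overt decompensated liver disease is something a clinical assessment may well detect, and the judgement exclusion is itself part of the list. The right word is *could*. These safeguards are nevertheless discretionary and carry no hepatic threshold, whereas 3.3.2 is categorical.

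Third, the renal half is largely covered. Section 4.5.1 requires all screening evaluations to be reviewed against eligibility before enrollment, so an eGFR below 30 found at screening can reasonably be treated as known, and dialysis is excluded separately. It would also be wrong to read the chronic kidney disease example in 4.1.1 as admitting patients below the limit. An inclusion example does not override an exclusion, and section 4.3.2.2 already expects some renal impairment among enrolled patients. What remains is that the eGFR calculation is not spelled out.

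**Conclusion.** The point holds, mainly for the liver. Section 3.3.2 promises the exclusion of severe hepatic impairment, and neither the exclusion list nor Appendix 4 contains a criterion that captures it when ALT and AST are at or below 3 × ULN. Enrollment of such a patient is possible, subject to investigator discretion. The renal issue is smaller: a limit exists, but its link to screening creatinine is not stated.

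The size cannot be derived. It is tempting to apply an assumed prevalence to the 366 patients, but the documents give neither the frequency of severe organ impairment in this population nor how often the discretionary safeguards would act. The number may be zero. The conclusion rests on comparing the texts and needs no prevalence.

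Alpha, power, sample size and the primary analysis are unaffected. What is affected is who may be randomised and repeatedly dosed, and how the studied population can be described.

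**What to change.** Reconcile Protocol 3.3.2 with the exclusion list in the synopsis, section 4.1.2 and SAP Appendix 1, in one of two ways:

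- **Make the list match the rationale.** Add the severe hepatic impairment exclusion that 3.3.2 states. The sponsor sets the definition, which can draw on the medical history and the bilirubin and albumin already collected at screening. For the kidney, state that the existing eGFR limit is assessed on the screening creatinine.
- **Make the rationale match the list.** If the sponsor intends to admit these patients, correct 3.3.2 to describe the population actually admitted.

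A hepatic exclusion without a definition would leave the same ambiguity, so the first option is complete only once the sponsor supplies one. No clinical threshold is proposed here.

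The cost is protocol and SAP wording, no additional test, and a few more screen failures under the first option. An amendment cannot change who has already been enrolled, and the blinded review for this protocol version already included data from 127 patients. The recorded history and screening chemistry would allow any affected patients to be identified and described in the report.

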3.3.3 Rationale for Control Group

It is not ethical to withhold active treatment from patients hospitalized with influenza, given the potential severity and poor outcomes in this patient group. NAIs are well-established and well-characterized antiviral agents used as the SOC in many patients hospitalized with influenza and are supported in published guidelines for antiviral treatment of these patients (Harper et al. 2009; Fiore et al. 2011). All patients in this study will receive a SOC NAI treatment (i.e., oseltamivir, zanamivir, or peramivir). In addition, patients will be randomized in a 2:1 ratio to receive baloxavir marboxil or its matching placebo. Therefore, at a minimum, all patients will be treated with a SOC NAI for influenza.

3.3.4 Rationale for Endpoints

There is no validated clinical end-point for assessing improvement in patients hospitalized due to influenza. Consequently, *three* measures of clinical improvement are used in this study: “*time to clinical improvement*” as the primary endpoint, “*response rates of the 6-point ordinal scale*” and “*time to clinical response*” as *key secondary endpoints*. *The primary and both key secondary endpoints will be tested in a hierarchical chain to control the experiment-wise error rate (alpha).*

The primary endpoint for this study will be the time to clinical improvement (TTCI), defined as time to hospital discharge or time to National Early Warning Score 2 (NEWS2) of ≤ 2 maintained for 24 hours, whichever occurs first. This endpoint will provide objective evidence of improvement in a patient’s condition, which is likely to be a reasonable surrogate to overall clinical status improvement.

The original NEWS was created in the United Kingdom by the Royal College of Physicians in 2012 to standardize the process of recording, scoring, and responding to changes in routinely measured physiological parameters in acutely ill patients. The score has been widely implemented across the National Health Service in the United Kingdom, and in other healthcare settings across the world. NEWS2 is a similar but updated score (Royal College of Physicians 2017) to incorporate an additional oxygen scale for patients at risk of hypercapnic respiratory failure (target oxygen saturation of 88%–92%, rather than the standard target of $\leq 96\%$).

Six physiological parameters are routinely recorded:

- Respiration rate
- Oxygen saturation
- Systolic blood pressure
- Pulse rate
- Level of consciousness and new confusion (ACVPU: A=alert, C=new confusion, V=responsive to voice, P=responsive to pain, U=unconscious)
- Temperature

In addition, a weighting score of 2 is added for patients requiring supplemental oxygen to maintain their prescribed oxygen saturation range.

NEWS2 was developed for patients aged ≥ 16 years; however, children aged 12–16 years have very similar physiological parameter ranges as adults. In this study, NEWS2 is not being used as an early warning system to identify patients who may need escalating levels of care; rather, it is being used to standardize vital sign collection which will facilitate setting severity levels for inclusion and demonstrating response to treatment. Most pediatric early warning scores are complex and designed to detect critical illness in younger children. For the purposes of this study, a patient achieving a NEWS2 of ≤ 2 is likely to represent a meaningful degree of clinical improvement (i.e., clinically stable and potentially eligible for discharge). Importantly as well, the method of statistical analysis and the selection of a clinically meaningful difference between treatment groups are possible for an endpoint of this design.

The *first* key secondary endpoint will be the proportion of patients per category in the 6-point ordinal scale at Day 7. The categories within this scale (see Section 4.5.16) reflect the clinical status of patients during their hospital stay. The clinical status should be assessed to reflect the most accurate condition of the patient from a medical perspective, to minimize the effects of administrative or non-medical factors (e.g., the hospital bed availability may lead to patients not being cared for in the ward most suitable for their condition). This endpoint has received considerable interest for use in this patient population. There is as yet no definition of a minimum clinically relevant difference between treatment groups; however, the 6-point ordinal scale will be used in

this study to investigate the change in clinical state of patients as the key secondary endpoint.

The second of the two key secondary endpoints will be “time to clinical response”. This endpoint is defined by the time to hospital discharge or the time to vital sign parameter stabilization. Vital sign stabilization is based on achieving a set temperature, combined with achieving a set oxygen saturation, plus two out of three other parameters related to respiratory status, blood pressure or heart rate (see Section 6.5).

This endpoint was defined in a previous intravenous zanamivir or oral oseltamivir clinical study, the largest randomized, double-blind clinical trial of any NAI in hospitalized patients with severe influenza to date (Marty et al. 2017). In the study by Marty et al., the “time to clinical response” (primary endpoint) was not met, and numerical non-significant differences were noted and warrant further investigation.

4. MATERIALS AND METHODS

4.1 PATIENTS

This study aims to enroll approximately 366 adult and adolescent patients. The study is designed to assess the safety and clinical activity of baloxavir marboxil when given in combination with a SOC NAI in patients hospitalized due to severe influenza.

4.1.1 Inclusion Criteria

Patients must meet the following criteria for study entry:

- Adult patients: Signed informed consent by any patient capable of giving consent, or, where the patient is not capable of giving consent, by his or her legal/authorized representative
- Adolescent patients not able to legally consent: written informed consent for study participation is obtained from patient’s parents or legal guardian, with assent as appropriate by the patient, depending on the patient’s level of understanding and capability to provide assent
- Age \geq 12 years at the time of signing the Informed Consent Form/Assent Form
- Ability to comply with the study protocol, in the investigator’s judgment
- Patients who require hospitalization for severe influenza or acquire influenza during hospitalization, the severity of which requires an extension of hospitalization
- Diagnosis of influenza A and/or B by a positive Rapid Influenza Diagnostic Test (RIDT) or reverse transcriptase-polymerase chain reaction (RT-PCR)

Positive results from local tests are acceptable if conducted within the 24 hours prior to screening.

A patient with a negative RIDT may be enrolled if influenza is suspected based on local surveillance data or if the patient reports contact with a known case of influenza within the prior 7 days and all other inclusion criteria are met

- The time interval between the onset of symptoms and randomization is within 96 hours

The onset of symptoms is defined as the time when the patient experiences at least one new general symptom (e.g., headache, feverishness or chills, muscle or joint pain, fatigue), respiratory symptom (e.g., cough, sore throat, nasal congestion), or fever.

- A score of ≥ 4 based on the NEWS2 (see [Appendix 3](#))
- Patients will require objective criteria of seriousness defined by at least one of the following criteria:
 - Requires ventilation or supplemental oxygen to support respiration
 - Has a complication related to influenza that requires hospitalization (e.g., pneumonia, CNS involvement, myositis, rhabdomyolysis, acute exacerbation of chronic kidney disease, asthma or chronic obstructive pulmonary disease [COPD], severe dehydration, myocarditis, pericarditis, exacerbation of ischemic heart disease)
- For women of childbearing potential: Agreement to remain abstinent (refrain from heterosexual intercourse):

Women must remain abstinent or use contraceptive methods with a failure rate of $< 1\%$ per year during the treatment period and for 28 days after the last dose of study treatment. Hormonal contraceptive methods must be supplemented by a barrier method.

A woman is considered to be of childbearing potential if she is postmenarcheal, has not reached a postmenopausal state (≥ 12 continuous months of amenorrhea with no identified cause other than menopause), and has not undergone surgical sterilization (removal of ovaries and/or uterus).

Examples of contraceptive methods with a failure rate of $< 1\%$ per year include bilateral tubal ligation, male sterilization, hormonal contraceptives that inhibit ovulation, hormone-releasing intrauterine devices, and copper intrauterine devices.

The reliability of sexual abstinence should be evaluated in relation to the duration of the clinical trial and the preferred and usual lifestyle of the patient. Periodic abstinence (e.g., calendar, ovulation, symptothermal, or postovulation methods) and withdrawal are not acceptable methods of contraception.

4.1.2 Exclusion Criteria

Patients who meet any of the following criteria will be excluded from study entry:

- Patients who have received more than 48 hours of antiviral treatment for *the current influenza infection* prior to screening
- Patients who have received baloxavir marboxil for the current influenza infection
- Known contraindication to neuraminidase inhibitors
- Patients hospitalized for exclusively social reasons (e.g., lack of caregivers at home)

- Patients expected to die or be discharged within 48 hours, according to the investigator's judgement
- Patients weighing <40 kg
- Patients with known severe renal impairment (estimated glomerular filtration rate <30 mL/min/1.73 m²) or receiving continuous renal replacement therapy, hemodialysis, peritoneal dialysis
- Patients with any of the following laboratory abnormalities detected within 24 hours prior to or during screening (according to local laboratory reference ranges:
 - ALT or AST level > 5 times the upper limit of normal (ULN)
 - OR
 - ALT or AST > 3 times the ULN and total bilirubin level > 2 times the ULN
- Pregnant or breastfeeding, or positive pregnancy test in a predose examination, or intending to become pregnant during the study or within 28 days after the last dose of study treatment
- Exposure to an investigational drug within 5 half-lives or 30 days (whichever is longer) of randomization
- Any serious medical condition or abnormality in clinical laboratory tests that, in the investigator's judgment, precludes the patient's safe participation in and completion of the study
- *Known hypersensitivity to baloxavir marboxil or the drug product excipients*

